5.6.3.4. Summary of Results by Time Point

Central laboratory values (in conventional (US) and international units), percent change from baseline, and/or when appropriate absolute change from baseline (in conventional and international units), for LDL-C, Total-C, HDL-C, fasting TG, non-HDL-C, Lp(a), Apo-B, Apo-A1 and ratio Apo-B/Apo-A1 (absolute change from baseline) at weeks 8, 12, 24, 48, 72, and 96 time points will be summarized by treatment group in both the ITT and mITT populations as described below:

- For lipids other than TG and Lp(a): LS mean and SE for each treatment group, obtained from the same MMRM models as used for endpoints above and including planned time points (see Section 5.6.3.1) and with raw values, changes from baseline, and percent change from baseline as response variable in the model as appropriate.
- For lipids other than TG and Lp(a): Observed data raw values, change from baseline (as applicable), and percent change from baseline response variables will be summarized by patient counts, mean and SD for each treatment group at all planned time points.
- For TG and Lp(a): mean and SE for each treatment group obtained from multiple imputation approach followed by the robust regression models as used for endpoints above and including planned time points (see Section 5.6.3.2) and with raw values or percent changes from baseline as response variable in the model as appropriate.
- For TG and Lp(a): Observed data raw values and percent change from baseline response variables will be summarized by patient counts, mean and SD for each treatment group at all planned time points.

5.6.4. Adjustment for Multiple Comparisons

Adjustments to the alpha level for the purposes of multiple testing are not applicable for this safety study. The exploratory neurocognitive and secondary efficacy lipid endpoints are supportive of the primary analysis and not hypothesis-testing. Any statistical testing is for descriptive purposes only (ie, any p-values provided are nominal).

5.7. Analysis of Safety Data

The summary of safety results will be presented by treatment groups (Praluent, placebo) on the safety population (Section 3.1). No formal inferential testing will be performed.

Summaries will be descriptive in nature. All summaries of safety results described below will be presented for each period respectively, unless otherwise noted.

General common rules

All safety analyses will be performed, unless otherwise specified, using the following common rules:

- Safety data in patients who do not belong to the safety population (i.e., exposed but not randomized) will be listed separately.
- The baseline value is defined as the last available value obtained up to the date and time of the first study treatment, except otherwise specified.
- PCSA values are defined as abnormal values considered medically important by the Sponsor according to predefined criteria/thresholds based on literature review and defined by the Sponsor for clinical laboratory tests and vital signs (PCSA version dated January 2009 [Appendix 10.3]). Considering that the threshold defined in the PCSA list for monocytes and basophils can be below the ULN, the following PCSA criterion will be used for the PCSA analysis of monocytes and basophils:
 - PCSA criterion for monocytes: >0.7 Giga/L or $>\text{ULN}$ (if $\text{ULN} \geq 0.7$ Giga/L).
 - PCSA criterion for basophils: >0.1 Giga/L or $>\text{ULN}$ (if $\text{ULN} \geq 0.1$ Giga/L).
- PCSA criteria will determine which patients had at least 1 PCSA during the TEAE period, taking into account all evaluations including nonscheduled or repeated evaluations.
- The treatment-emergent PCSA denominator by treatment group for a given parameter will be based on the number of patients assessed for that given parameter at least once during the TEAE period.
- All measurements, scheduled or unscheduled, fasting or not fasting, will be assigned to analysis windows defined in Appendix 10.2, Table 2 in order to provide an assessment for week 8 to week 96 time points.
- For quantitative safety parameters including central laboratory measurements and vital sign scores, descriptive statistics will be used to summarize results and change from baseline values by visit, the last on-treatment value and the worst on-treatment value. The last on-treatment value is defined as the last post-baseline value collected during the respective treatment period (as defined in

Section 4.7.1). The worst on-treatment value is defined post-baseline as the nadir and/or the peak value collected during the respective treatment period, according to the direction (minimum or maximum) of the abnormality as defined in the PCSA list.

- For exploratory purposes, specific safety analyses could also be provided according to up-titration status, ie, according to whether the patients remained on the alirocumab 75 mg Q2W doses or whether they were up titrated to 150 mg Q2W. These analyses will be exploratory and descriptive (no formal comparison per dose) as it is expected that there could be inherent differences in the baseline characteristics between those patients titrating to 150 mg Q2W and those remaining on the alirocumab 75 mg Q2W doses. In order to reduce the bias of this analysis, the period before the up-titration time point (planned at Week 12) will be analyzed separately since only the alirocumab 75 mg Q2W doses are proposed for this time period and consequently the early events occurring before Week 12 can only be attributed to those doses. Therefore, the descriptive analysis per dose will include any safety events occurring from the first injection post Week 12 IVRS/IWRS transaction to the end of the TEAE period. Baseline characteristics of patients receiving each dose will be summarized.
- Analyses performed according to diabetes status will be done considering diabetic patients as patients with either type 1 or type 2 diabetes in the medical history e-CRF page (regardless of the ongoing status).

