4.7.1.1. Adverse Events and Serious Adverse Events

Adverse events (including serious adverse events (SAE), AEs causing permanent treatment discontinuation, deaths, and AEs of special interest) are recorded from the time of signed informed consent until the end of study. All AEs diagnosed by the Investigator will be reported and described.

All AEs will be dictionary coded by “lowest level term (LLT)”, “preferred term (PT)”, “high level term (HLT)”, “high level group term (HLGT)” and associated primary “system organ class (SOC)” using the version of MedDRA in effect at the time of database lock for the analysis.

Adverse Event Observation Period

- Pre-treatment AEs are AEs that developed or worsened or became serious during the pre-treatment period.
- Treatment-emergent adverse events (TEAEs) are AEs that developed or worsened or became serious during the TEAE period.
- Post-treatment AEs are AEs that developed or worsened or became serious during the post-treatment period.

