4.7.1.2. Adverse Events of Special Interest

Adverse events of special interest (AESI) are AEs (serious or non-serious) required to be monitored, documented, and managed in a pre-specified manner as described in the protocol.

In this study, AESI are the following (their complete descriptions are provided in the protocol):

- Local injection site reactions, selected using an e-CRF specific tick box on the AE page;
- Allergic events:
- General allergic events will be tabulated. Events will be selected using standardized MedDRA query (SMQ) “hypersensitivity” (broad and narrow) excluding the preferred terms linked to local injection site reactions (i.e. preferred terms containing “injection site” or “infusion site”)
- ALT ≥ 3 ULN in the case baseline ALT < ULN or ALT ≥ 2 times the baseline value in the case baseline ALT \geq ULN, selected using laboratory data;
- Neurologic events selected using SMQs “demyelination” (broad and narrow), “peripheral neuropathy” (broad and narrow), and “Guillain-Barre syndrome” (broad and narrow) excluding the following preferred terms: “acute respiratory distress syndrome”, “asthenia”, “respiratory arrest” and “respiratory failure” and including selected PTs from SMQ “optic nerve disorders” (see Appendix 10.5, [Table 3](#) for the list of terms)
- Symptomatic overdose with investigational medicine product, selected using HLT “Overdose” and the tick box “Symptomatic Overdose” in the e-CRF AE page.
- Pregnancy of female patient/subject (including male subject’s partner), selected using appropriate MedDRA codes.
- Neurocognitive events:
 - Selected using a company MedDRA query (CMQ), based on the following 5 HLTGs: “deliria (including confusion)”, “cognitive and attention disorders and disturbances”, “dementia and amnestic conditions”, “disturbances in thinking and perception”, and “mental impairment disorders”.
 - A second grouping of terms for neurocognitive events was defined based on Regulatory Agency request (FDA CMQ) (see Appendix 10.5, [Table 4](#) for the list of terms)
- Cataract using HLT “Cataract conditions”
- New onset of diabetes (NOD) will be assessed in patients without diabète at baseline: The definition of new onset of diabetes (NOD) will be the following:
 - Type 1 or type 2 diabetes TEAE (grouping of Medical Dictionary for Regulatory Activities [MedDRA®] terms in Appendix 10.4, [Table 7](#))

and/or

- At least 2 values of HbA1c $\geq 6.5\%$ during the TEAE period

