NOTE: For patients with only a single measurement available during the TEAE period, a single value $\geq 6.5\%$ will be considered and qualify the patient as NOD by default.

For patients with several HbA1c measurements but only with the last one $\geq 6.5\%$, this single value $\geq 6.5\%$ will be considered and qualify the patient as NOD by default

and/or

- At least 2 values of fasting plasma glucose (FPG) ≥ 126 mg/dL (7.0 mmol/L)

NOTE: For patients with only a single measurement available during the TEAE period, a single value ≥ 126 mg/dL (7.0 mmol/L) will NOT be considered and will NOT qualify the patient as NOD

For patients with several FPG measurements but only with the last one ≥ 126 mg/dL (7.0 mmol/L), this single value ≥ 126 mg/dL (7.0 mmol/L) will NOT be considered and will NOT qualify the patient as NOD

Analyses of NOD events will also be provided using the tick box on the e-CRF AE page as an exploratory approach in patients without Diabète at baseline.

In addition, the following grouping of events will be provided:

- Hepatic disorder events using SMQ “Hepatic disorder”
- Diabetes mellitus or diabetic complications using 1/ the HLGT “diabetes complications” (including PTs pertaining to the secondary SOC included in the HLGT), 2/ the HLT “diabetes mellitus”, 3/ the HLT “carbohydrate tolerance analyses (incl diabetes)” excluding PTs “blood glucose decreased” and “Glycosylated haemoglobin decreased” and 4/ from the HLT “Hyperglycaemic conditions NEC” only the following PTs “hyperglycaemia”, “Hyperglycaemic unconsciousness” and “Hyperglycaemic seizure”

Neurocognitive Events of Special Interest

Neurocognitive events are defined in this study as AESI, specifically, neurocognitive AEs (serious or nonserious) required to be monitored, documented, and managed in a pre-specified manner as described in this protocol. The neurocognitive events will be adjudicated by the neurocognitive events review committee which is composed of experts in the field of cognition, independent from the sponsor and the investigators. This committee will be responsible for defining, validating, and classifying (in a blinded fashion) AEs of interest possibly related to cognition impairment. A charter and an operational manual will specify the procedures and criteria used for review of these events.

The committee will adjudicate whether a neurocognitive event identified by investigator or the CMQs is indeed a neurocognitive event (Yes/No).

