4.9. Anti-Drug Antibody Variables

Anti-drug (Praluent) antibody (ADA) are assessed at baseline (before the first study treatment injection), at weeks 48 and 96. ADA measurements will be assigned to the analysis windows as defined in Appendix 10.2. As appropriate, patient frequencies and percentages will be depicted, and the percentages will be calculated based on the ADA population.

The following variables will be described:

- ADA response (Positive or Negative). For ADA positive:
 - Titer levels
 - Neutralizing status (Positive or Negative)
- Pre-existing positive ADA defined as patients with positive ADA response at baseline with less than 4-fold increase in titer in the post-baseline period
- Treatment-emergent positive ADA response defined as 1) Patients with no ADA positive response at baseline but with any positive response in the post-baseline period or 2) Patients with a positive ADA response at baseline and at least a 4-fold increase in titer in the post-baseline period. For treatment-emergent positive ADA, the following categories for ADA duration will be applied:
 - A persistent positive response is a treatment-emergent ADA positive response detected in at least 2 consecutive post-baseline samples separated by at least a 12-week period
 - An indeterminate duration positive response is defined as ADA present only at the last sampling time point
 - A transient positive response is defined as any treatment-emergent positive ADA response that is neither considered persistent nor indeterminate

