The number and percentage of patients with a post-baseline seroconversion for hepatitis C test will be provided by treatment group in post-baseline (including the TEAE and post TEAE periods) as well as in the TEAE period alone. Post-baseline seroconversion is defined for patients with a negative baseline status who had either a “positive RNA” or a “confirmed positive antibody with negative RNA” post-baseline status as defined in the table below. Other situations require case by case evaluation and will be described individually if relevant.

The status as regards hepatitis C virus for a patient will be defined as follows for all evaluations (baseline and post-baseline).

Table 1: Definition of the patient status regarding hepatitis C virus

		Hepatitis C Antibody test result			
		Negative		Positive	
Reflexive test ^a – hepatitis C RNA test	Not available or HCV RNA not detected	HCV RNA detected	HCV RNA not detected ^b	HCV RNA detected	Not available
Hepatitis C status – label	Negative	Positive RNA	Negative ^b	Positive RNA	Positive Ab – no RNA available

^a test performed at the same time or after the antibody test in pre-treatment period (for baseline evaluation), or post-baseline, respectively

^b For post-baseline evaluation, a second antibody test with a different type of assay is to be done at the same date or after the first antibody test. The result of this test will modify the final hepatitis C status of the patient in some cases (see details in the text below the table)

The baseline evaluation will be based on tests performed during the pre-treatment period.

In case of multiple hepatitis C tests available for the post-baseline evaluation, the positive status of the patient will be defined as follows:

- “Positive RNA” status if at least 1 post-baseline positive RNA is detected, regardless of status of the patient at the end of treatment.
- Else “Positive Ab – no RNA available” status if no post-baseline reflexive RNA test is available for at least 1 post-baseline positive antibody test.

If no antibody test is available or with “indeterminate” as result pre-treatment or post-baseline respectively, the RNA test (if available) will be used alone to determine the status of the patient. If no RNA test is available then the hepatitis C status of the patient will be missing.

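### New-onset diabetes: the laboratory criteria ignore pre-dose values, so diabetes missing from medical history is counted as new

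*SAP*

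**What the plan says.** New onset of diabetes is one of the adverse events of interest listed in Protocol 7.6.4.5. SAP 4.7.1.2 sets the population ("New onset of diabetes (NOD) will be assessed in patients without" diabetes at baseline) and three alternative routes to a case:

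- a diabetes term reported as a TEAE;
- two or more HbA1c results of 6.5% or higher in the TEAE period. If there is only one result, or only the last is raised, that single value "will be considered and qualify the patient as NOD by default";
- two or more fasting plasma glucose (FPG) results of 126 mg/dL or higher. A single or last-only raised value does not count.

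Section 4.7.1.2 does not say how absence of diabetes at baseline is established. The general rules in SAP 5.7 do, for analyses by diabetes status: they are done "considering diabetic patients as patients with either type 1 or type 2 diabetes in the medical history e-CRF page", whether or not the condition is ongoing. An additional approach, labelled exploratory, is also planned: "Analyses of NOD events will also be provided using the tick box on the e-CRF AE page".

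Pre-dose measurements exist. Protocol Table 1 schedules HbA1c at screening, and chemistry (which includes glucose) at screening and day 1. SAP 4.1 tabulates a baseline HbA1c class of 6.5% or more, but the NOD rule does not use it.

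**The concern.** An onset criterion has to separate a new abnormality from one already present. Here the laboratory routes look only at post-dose values, and entry to the at-risk set depends only on what was written in the history. Diabetes that is visible in the pre-dose samples but not recorded as history enters as non-diabetic and leaves as a new case.

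Elsewhere the SAP conditions comparable events on baseline. The ALT event uses a multiple, "times the baseline value in the case baseline ALT" is already at or above the upper limit. For hepatitis C, "Post-baseline seroconversion is defined for patients with a negative baseline status". For anti-drug antibodies, the first category of treatment-emergent response is "Patients with no ADA positive response at baseline but with any positive response in the post-baseline period".

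What is at stake is the reading of a named safety event. Prevalent cases raise the NOD count and percentage in both arms and dilute any ratio towards 1, which is the unhelpful direction when looking for harm.

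**Working it through.** **Reading the rules together.** The documents give no NOD rate, so there is no plan figure to reproduce. Take a patient with no diabetes in medical history and HbA1c of 6.8% at screening, week 24 and week 48.

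1. Status under SAP 5.7: not diabetic, because there is no history entry.
2. HbA1c route in SAP 4.7.1.2: two qualifying post-dose values by week 48.
3. Result: new onset, although nothing has changed.

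Nothing in the plan prevents this. Medical history is scheduled only at visit 1, the visit at which screening HbA1c is drawn (Protocol Table 1), and no rule requires the history to be updated once the result is known. No exclusion criterion in Protocol 4.2.2 concerns HbA1c or glucose. Diabetes found at screening could be recorded as a pre-treatment AE and not as history, and the patient would still count as non-diabetic.

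The AE-term route does not share the defect, since TEAEs "are AEs that developed or worsened or became serious during the TEAE period". The tick-box analysis shares the population definition but not the automatic laboratory trigger.

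**Chance that such a patient is counted.** Let p be the assumed chance that each post-dose HbA1c is 6.5% or more. A case needs at least two such values, or only the last. With n independent values:

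q = 1 − (1−p)^n − (n−1)·p·(1−p)^(n−1)

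For the four scheduled values (weeks 24, 48, 72 and 96), q = 1 − (1−p)^4 − 3p(1−p)^3:

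| p | 0.3 | 0.5 | 0.7 | 0.9 |
|---|---|---|---|---|
| q | 0.451 | 0.750 | 0.935 | 0.997 |

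At p = 0.5: 1 − 0.0625 − 0.1875 = 0.75. With one or two values, or fully correlated values, q = p. So p = 0.5 gives q between 0.50 and 0.75.

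**Effect on the reported figures.** Let b be the assumed share of at-risk patients with unrecorded prevalent diabetes. Assume a true placebo incidence of 5% and a true difference of 2.5 points among the rest (true ratio 0.075/0.05 = 1.50).

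- Prevalent cases per 1000 at risk = 1000·b·q
- Placebo rate seen = b·q + (1−b)·0.05
- Prevalent share = b·q / placebo rate seen
- Difference seen = 0.025·(1−b)
- Ratio seen = 1 + difference seen / placebo rate seen

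| b | q | Prevalent per 1000 | Placebo seen | Prevalent share | Difference seen | Ratio seen |
|---|---|---|---|---|---|---|
| 2% | 0.50 | 10 | 5.9% | 17% | 2.45 points | 1.42 |
| 2% | 0.75 | 15 | 6.4% | 23% | 2.45 points | 1.38 |
| 4% | 0.50 | 20 | 6.8% | 29% | 2.40 points | 1.35 |
| 4% | 0.75 | 30 | 7.8% | 38% | 2.40 points | 1.31 |
| 6% | 0.50 | 30 | 7.7% | 39% | 2.35 points | 1.31 |
| 6% | 0.75 | 45 | 9.2% | 49% | 2.35 points | 1.26 |

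A second set of assumptions (b of 1% to 5%, q of 0.6 to 0.9, true control incidence of 3% to 6%, true ratio 1.3) gives a prevalent share of 9% to 61% and an observed ratio of 1.27 down to 1.12.

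**The case against.** The strongest reply is that other planned outputs already show much of this.

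- HbA1c change from baseline is defined (SAP 4.8), and HbA1c is summarised by arm, visit and baseline diabetes status (SAP 5.8).
- Glucose is analysed by diabetic status and by baseline PCSA status (SAP 5.7.2). The fasting PCSA limit is 7 mmol/L, the same threshold as the FPG route.
- TEAEs in the diabetes grouping are split by baseline status (SAP 5.7.1).
- Investigators review all laboratory values (Protocol 7.6.4.3).

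These outputs are real and would help a careful reader. But they use the same history-based status or answer a different question, and none corrects the NOD count. The baseline HbA1c table pools known diabetics with everyone else, so it gives only a loose upper bound on the affected patients.

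It can also be said that the rule in SAP 5.7 is written for analyses by diabetes status and is not cited in 4.7.1.2. Applying it to NOD is indeed an inference. It is the only definition available, however; without it the at-risk population is undefined.

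The SAP does report some thresholds regardless of baseline, for example HbA1c PCSA in 5.8. Those tables do not claim to show onset.

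Three points stand. The inputs to the illustration have no anchor in the documents, and b could be close to zero: diabetes is a qualifying risk factor (Protocol 4.2.1) and a history item of specific interest (SAP 4.2), so unrecorded cases may be uncommon. Misclassification should balance by randomisation. The analysis is descriptive, with no planned test (SAP 5.7).

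**Conclusion.** The concern holds. Followed exactly, the SAP counts prevalent, unrecorded diabetes as new onset through its HbA1c and FPG routes. The defect is confined to those routes.

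Its size is unknown. Under the first set of assumptions, 10 to 45 cases per 1000 at-risk patients per arm would be misreported and a true ratio of 1.50 would read as 1.26 to 1.42, while a true difference of 2.5 points would read as 2.35 to 2.45. The range depends wholly on the assumed p, b, incidence and difference, and on balanced misclassification.

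The primary endpoint is not affected. This should be corrected before database lock because the event is named in the protocol and the correction is cheap; it does not threaten the trial's main conclusion.

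**What to change.** In SAP 4.7.1.2, define the NOD at-risk set as patients who meet all of these:

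- no diabetes in medical history;
- baseline HbA1c below 6.5%;
- not two pre-dose fasting glucose values of 126 mg/dL or more.

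This follows the SAP's own logic: a sole HbA1c value qualifies, a single FPG value does not. Where a pre-dose HbA1c or fasting glucose is missing, classify on what remains. Use this set as the NOD denominator, list the excluded patients by arm, and keep the history-only definition as a sensitivity analysis. As a wording tidy-up, add the TEAE period to the FPG criterion; only the note beneath it now says so.

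The cost is SAP text and one listing, with no new samples. There are three drawbacks. The denominator shrinks by an amount the documents do not allow to be estimated. Exclusion rests on one scheduled HbA1c value, so some patients near the threshold will be removed who might not be confirmed on repeat, or in whom real progression could appear; the history-only sensitivity analysis shows that effect. The protocol's visit and sampling instructions (7.2, 7.6.3, 7.6.4.3) do not require fasting, so two fasting pre-dose glucose values may not exist for every patient, and the missing-value rule must then apply.
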